9.4 PATIENTS REFUSING PARTICIPATION

Patients, who meet all inclusion criteria but do not wish to participate, should be registered. Date, hospital patient identification number, gender, location of tumor, type of operation, ASA class, TNM stage, Dukes stage and a short reason for refusal should be noted.

Possible reasons: - objects to laparoscopic operation
 - objects to conventional operation
 - objects to participate in medical studies

9.5 NON INCLUDED & EXCLUDED PATIENTS

All patients suspected of having rectal cancer, who are considered for operation, should be registered. Thus patients who do not meet the inclusion criteria, as well as patients excluded after randomization, should be registered concerning date, hospital patient identification number, gender, location of tumor, type of operations, ASA class, TNM stage and Dukes stage. In addition to this registration, a short reason for non-

inclusion or exclusion should be noted.

For example:

- metastases
- inoperability
- no adenocarcinoma in resected specimen
- laparoscopic surgery contraindicated (include reason)

10 RANDOMIZATION

Once eligibility has been established and patient details have been logged, the patient will be allocated to either laparoscopic or conventional operation. Randomization will be performed by computer at time of randomization. Randomization will be balanced and stratified by participating center, resection type, radiotherapy and sex. When patients are not subjected to the treatment modality as randomized, data will be analyzed on an "intention to treat basis" (once randomized, patients will not be excluded or changed groups because of conversion or type of resection).

Randomization for all centers will be done through internet:

www.color2.org (click "investigators")

11 PERI-OPERATIVE CARE & EXAMINATIONS

11.1 PRE-OPERATIVE WORK-UP

Colonoscopy or lateral barium enema radiography of the complete colon is performed to exclude concomitant tumors. The entire colon should be imaged either pre-operatively, or within 3 months after surgery. Biopsies are mandatory. Lateral barium enema radiography or rigid rectoscopy should be performed to assess the localization of the cancer in the rectum. CT or MRI of the pelvis is performed to show its relation to surrounding structures. The radiologist should report the estimated distance between the tumor margin and the endopelvic fascia. Endorectal sonography is optional. Pre-operative work-up should include imaging of chest and liver. CT scan of both thorax and abdomen is the preferred preoperative screening to assess metastatic disease.

11.2 PRE-OPERATIVE CARE

Bowel preparation, antibiotic prophylactics and deep venous thrombosis prophylactics will be according to local standards and should be standardized by each center for all of their patients. Preoperative care should be the same in each treatment arm throughout the trial.

11.3 INTRA-OPERATIVE CARE

Anesthetic care should be standardized by each center for all of their patients in each treatment arm throughout the trial. New anesthesiology protocols can be introduced during the study, when these protocols apply to both arms.

11.4 POST-OPERATIVE CARE

Analgesic care and allowance of restoration of diet will be according to local standards, but this should be standardized for all patients in each treatment arm throughout the trial.

12 SURGICAL PROCEDURE

12.1 LAPAROSCOPIC TECHNIQUE [34]

Laparoscopic dissection of the mesorectum is mandatory to qualify the procedure as a "laparoscopic TME". The level of transection of the inferior mesenteric artery is up to the surgeon's preference. Both right and left hypogastric nerves should be preserved. The splenic flexure should be mobilized when undue tension at the anastomoses is likely. Other aspects of the surgical procedure such as type of anastomoses, use of diverting ileostomy and drainage of surgical field are up to the discretion of the surgeon.

12.2 CONVERSION

Conversion is defined as a change in operative approach to achieve the final goal and will be at the discretion of the individual surgeon for concerns of patient safety, technical difficulties, inability to complete the planned operation for sphincter sparing or associated conditions requiring treatment. Utilizing the extraction site for transverse stapler insertion to accomplish the distal anastomosis will not be considered a conversion. Identification of any grossly visible positive margins or extension into adjacent organs will mandate conversion to an open procedure. Completion of the pelvic dissection through open surgery will be considered conversion. Conversion is defined as a fascial incision longer than 10 cm, utilized to achieve anything other than specimen extraction. (Largest handport size is 8 cm)

13 HISTOPATHOLOGY.

All resected specimens are analyzed by the pathologist. Macroscopical assessment of the quality of mesorectal dissection will be scored in 3 grades.

- Complete: intact mesorectum with only minor irregularities of the mesorectal surface. No defect is deeper than 5 mm. No coning towards the distal margin of the specimen. Smooth circumferential resection margin on slicing.
- Partial incomplete: the majority of the mesorectum has been removed. Moderate coning of the specimen towards the distal margin. At no site is the muscularis propria visible with the exception of the area of the insertion of the levator muscles. Moderate irregularity of the circumferential resection margin.
- Incomplete: mesorectum with defects down onto muscularis propria and/or very irregular circumferential resection margin, coning.

The unopened resected specimen is received fresh, opened anteriorly except in the area of the tumor where the full circumference of the bowel should be left intact and pinned under gentle tension to a cork board for fixation in formalin. After fixation, the peritoneal reflection is identified and the relative position of the tumor noted i.e. below, partially covered by peritoneum or totally covered by peritoneum. Areas covered by peritoneum are inspected for serosal penetration and if apparent are sampled separately. Tumors completely covered by peritoneum are handled in the routine manner for colonic specimens, whereas those with a retroperitoneal component are subjected to close scrutiny for circumferential margin involvement by tumor. The site of the tumor is sliced as thinly as possible including up to 2 cm above and below, and laid out on a flat surface for macroscopic inspection.

The extent of tumor involvement of the perirectal tissue is assessed with particular attention being paid to the circumferential resection margin. The maximum extent of tumor spread from the outer limit of the muscularis propria is measured using a ruler. This should be to the edge of tumor's greatest distance of penetration from the muscular wall, be it direct, discontinuous, and vascular or lymph node involvement. Area or areas of involvement can usually be seen with the naked eye and any suspicious area or areas should be sampled for histology. One block should be sufficient, but up to six might need to be taken in cases with extensive spread before it is possible to be certain that all the margins are free of tumor. On average four blocks will suffice for the majority of tumors. The circumferential resection margin of the block should be marked with India ink to demarcate it on histology and rule out false positive tumor involvement of a tissue margin caused by poor embedding practice.

The specimen is now turned over, so the mucosal aspect faces downwards and the retroperitoneal/mesenteric faces upwards. The C node is identified and sampled and the whole of the specimen, from the proximal margin, (i.e. that nearest the surgical ligature of the inferior mesenteric artery, down to the previously excised tumor segment) is sliced serially down to the external aspect of the muscularis propria. Similarly, the segment of the rectum below the tumor is also serially sliced. Whilst incising the mesentery and the mesorectum, lymph nodes and tumor deposits should be identified and sampled. Metastases and lymph nodes adjacent to the circumferential margin should be sampled "en-bloc" with the resection margin, which again should be identified by painting with India ink.

Lymph nodes further than 1 cm from the circumferential resection margin or present in the mesentery of the sigmoid colon may be sampled in a routine fashion. If the tumor is close to the distal resection margin (i.e. < 2 cm away or in a bulky or poorly differentiated tumor < 5 cm away) then of course this margin should also be sampled.

Accurate measurement of the minimum distance between tumor and circumferential resection margin should

be performed by microscopy on the haematoxylin and eosin stained slide using the Vernier scale on the microscope stage. Shrinkage of tissue occurs during processing but this does not materially affect the accuracy of this measurement. Assessment by microscopy is preferred as a florid peri-tumoral inflammatory reaction or fibrosis will lead to an overestimate of macroscopic tumor spread. Macroscopic measurements are accurate enough for the distance from the muscular wall to the edge of the tumor as this measurement is only used for the comparison of local recurrence rates between surgeons.

13.1 TUMOR DEPOSITS

Sometimes tumor deposits are present without the structure of a lymph node. To avoid that the patient is incorrectly classified as node negative, please pay attention to the WHO definition: "a tumor nodule > 3 mm across in the connective tissue in the lymph drainage area of a primary tumor without histological evidence of residual lymph node in the nodule is classified in the N category as a regional lymph node metastasis. However a tumor nodule of <3mm is classified in the T category, i.e. discontinuous extension".

13.2 NUMBER OF LYMPH NODES

The exact number of lymph nodes and the lymph nodes along the vascular trunk are not always mentioned in the pathology report. To be able to compare the number of examined and the number of positive lymph nodes between the laparoscopically and open operated group, these two numbers should always be mentioned.

13.3 CIRCUMFERENTIAL MARGIN

A circumferential margin of < 2 mm is considered as positive. Since the margin of 2 mm is crucial, it should always be mentioned that this margin is less than 2 mm (positive) or more than 2 mm (negative). Sometimes we read "circumferential margin is 2 mm". In the database we can distinguish between "true" positive circumferential margins and 0 to 2-mm circumferential margins. When a positive lymph node is closer to the circumferential margin than the tumor itself, the margin between the positive node and the margin should be registered. The < 2 mm circumferential margin is crucial for the classification in R0 or R1. Therefore the exact margin should be expressed in two digits instead of one, since differentiation between 0.21 cm (R0) or 0.20 cm (R0) or >0.19 cm (R1) is crucial.

13.4 R-CLASSIFICATION

TNM and pTNM describe the anatomical extent of cancer in general without considering treatment. The residual tumor (R) classification deals with tumor status after treatment. It reflects the effects of treatment, influences further therapeutic procedures and is a strong predictor of prognosis. This R classification must be differentiated from the completely different Japanese R classification, which classifies tumor resections according to the extent of lymph node dissection. The Japanese Joint Committee for TNM classification decided in 1993 to use the symbol D to classify the extent of lymph node dissection in place of R in the coming editions of their General Rules (Japanese Research Society for Gastric Cancer 1993) to avoid confusion with the Residual Tumor Classification of TNM.

In the R classification, not only is local-regional residual tumor to be taken into consideration, but also distant residual tumor in the form of remaining distant metastases. R0 corresponds to complete remission or resection for cure. It is appropriate for cases in which residual tumor cannot be detected by any diagnostic means. R0 classification, therefore, does not exclude non-detectable residual tumor that may give rise to tumor recurrence or metastasis during follow-up. R0, in fact, corresponds to no detectable residual tumor and is not identical to cure.

The R classification can be used following surgical treatment alone, after radiotherapy alone, after chemotherapy alone or following multimodal therapy. After non-surgical treatment, the presence or absence of residual tumor is determined using clinical methods. Following surgical treatment, the R classification is possible through close cooperation between the surgeon and pathologist in a two-step process.

In the R0 group there may be M0 cases as well as M1 cases. In the latter, not only the primary tumor, and its lymphatic drainage but also the distant metastasis must be removed completely. Within the M1 group, there are statistically significant differences in relation to the R classification.

In tumor resection specimens with formal lymphadenectomy the "marginal" lymph node is the one near the resection line that is most distant from the primary tumor. Involvement of such "marginal" or "apical" nodes does not influence the R classification.

Difficulties arise in case of removal of the tumor in two or more parts and not "en bloc". Without an exact and reliable topographical orientation the pathologist cannot make a definitive assessment of the resection line. In these cases the classification Rx (presence of residual tumor cannot be assessed) is appropriate.

Positive cytology on lavage of the peritoneal cavity performed during staging laparoscopy or immediately after opening the abdomen (beginning of laparotomy) corresponds to M1, and is classified R1, even if there is no other evidence of residual tumor. This is based on the worse prognosis of such cases in comparison to those with negative cytology.

14 POST-OPERATIVE TREATMENT

14.1 PRE-OPERATIVE

Pre-operative adjuvant radio and/or chemotherapy may be part of the treatment of rectal carcinoma. Different schedules of preoperative radio- and/or chemotherapy may be used in trial patients, according to local standards and surgeons preference. Protocols for pre-operative adjuvant therapy should be equal in both treatment arms. Radiation protocols should be made known to the main coordinating center. Any changes in these protocols during the study period should be reported to and approved by the protocol committee.

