3.4 STATISTICS & RANDOMIZATION

Using log rank statistics with a power of 80 % and a type I error of 5%, 1275 patients are needed to detect a difference between both treatment arms of 5% in locoregional recurrence rate 3 years postoperatively, assuming a 10% recurrence rate in the open group. Randomization will be 2:1, laparoscopic versus open resection respectively. Analyses will be on "intention to treat" basis. Randomization is stratified for each participating center, planned procedure, radiotherapy and sex.

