4.5 ADJUVANT THERAPY

Extensive studies have been performed throughout the years to investigate the efficiency of many different regimes in controlling local recurrence. With the rise of the TME procedure, with its low recurrence rate, it is now reinvestigated what adjuvant therapy is best in optimizing local recurrence rates and long-term survival. Survival benefits for most regimes have to be proven again and benefits of adjuvant therapy have to be weighed against additive morbidity. In a recent publication, Kapiteijn et al showed that significantly less local recurrences occur after short preoperative radiation with 5*5 Gy in patients with rectal cancer (overall recurrence rate 8.2 vs. 2.4 respectively)[1]. Although no survival benefit was found, this might be caused by the relatively short follow-up of 2 years. The operative procedure was extensively standardized and

Post-operative chemotherapy is not standard treatment in rectal cancer. Chemotherapy is predominantly applied in randomized clinical trials.

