5 STUDY DESIGN

This trial is a randomized, international, multi-center study comparing laparoscopic and conventional resection for rectal cancer. Patients will be accrued by the participating hospitals of the COLOR II study group. The COLOR II study group is an international group of surgeons with interest and expertise in laparoscopic and colorectal surgery. Since 1997 the COLOR I study group has performed and almost completed a large international randomized controlled trial comparing laparoscopic to open surgery for colon cancer. Many centers of the COLOR I study group will join the COLOR II study group.

The design involves allocation of all suitable consecutive patients with rectal carcinoma to either of the two procedures at a randomization ratio of 2:1, in favor of the laparoscopic procedure. Excluded are patients with a carcinoma treated by local resection and palliative resections. The trial will be stratified according to participating center, resection type, preoperative radiotherapy and sex.

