17.2 DATA COLLECTED DURING PRE-OPERATIVE PERIOD

- ASA class
- length and weight
- number of previous abdominal operations
- date of diagnosis
- location of tumor
- proposed type of resection
- previous radiotherapy of the pelvis
- preoperative radiotherapy

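### Radiotherapy is a randomization stratum but is not among the items entered at randomization, so the protocol does not secure that the pre-operative therapy decision precedes knowledge of the arm

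*Protocol*

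**What the plan says.** Three sections of the protocol make radiotherapy a stratification factor. Section 5: "The trial will be stratified according to participating center, resection type, preoperative radiotherapy and sex". Section 10: "Randomization will be balanced and stratified by participating center, resection type, radiotherapy and sex". Section 3.4: "Randomization is stratified for each participating center, planned procedure, radiotherapy and sex". Only section 5 says that pre-operative radiotherapy is meant.

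On timing, section 10 states: "Once eligibility has been established and patient details have been logged, the patient will be allocated". It ties allocation to eligibility and logged details and does not mention the radiotherapy decision.

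Section 17.1 lists what the clinician enters through the internet at randomization: eligibility, randomizing physician, hospital, planned operation, sex, date of birth and clinical TNM stage. Radiotherapy is not there. Section 17.2, the pre-operative data, lists "preoperative radiotherapy", and the case record form asks for it as item 16 on the pre-operative page. Pre-operative chemotherapy is item 16a on that page.

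On who chooses the therapy, section 14.1 says: "Different schedules of preoperative radio- and/or chemotherapy may be used in trial patients, according to local standards and surgeons preference". The next sentence sets a limit: "Protocols for pre-operative adjuvant therapy should be equal in both treatment arms". Radiation protocols must be made known to the coordinating center, and changes need approval by the protocol committee.

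Section 4.5 cites a randomized trial of short pre-operative radiotherapy with "overall recurrence rate 8.2 vs. 2.4 respectively", at a follow-up it describes as relatively short (2 years).

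**The concern.** A stratum works only if its value is known and entered before the allocation is generated. Here the stated design relies on radiotherapy status, while the listed procedure never collects it at that moment. The surgeon cannot be blinded to the operation. If the decision on pre-operative therapy, or its schedule, is taken or revised after the arm is known, it can depend on the arm.

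The primary endpoint is locoregional recurrence at 3 years, and the protocol itself reports a large effect of radiotherapy on local recurrence. Arm-dependent use would mix the effect of radiotherapy into the comparison of the two operations. Analysis by intention to treat would carry that mixture into the result. Adjusting for therapy actually received would condition on something that happened after randomization and would not repair it. More use in the laparoscopic arm would push toward the conclusion that recurrence is not increased. More use in the open arm would push against it.

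**Working it through.** **1. Strata against randomization entries**

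| Factor | Stratum (3.4, 5, 10) | Entered at randomization (17.1) | Recorded elsewhere |
|---|---|---|---|
| Center | yes | yes (hospital) | form item 1 |
| Resection type | yes | yes (planned operation) | 17.2, form item 14 |
| Sex | yes | yes | form item 4 |
| Pre-operative radiotherapy | yes | **no** | 17.2, form item 16 |
| Radiotherapy schedule | no | no | form item 16 |
| Pre-operative chemotherapy | no | no | form item 16a |

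Three of the four strata can be formed from the section 17.1 entries, and radiotherapy cannot. The identification page of the case record form (items 1 to 6A), which holds the randomization date and assigned procedure, does not carry it either. Nothing states whether the stratum is planned or received radiotherapy.

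**2. The plan's own sample size (section 19.1)**

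Inputs: 10% recurrence in each arm, margin 5 points, two-sided 95% limits, 80% power, 2:1 allocation.

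Open arm: n = (1.960 + 0.842)² × (0.10×0.90 + 0.10×0.90/2) / 0.05² = 7.85 × 0.135 / 0.0025 ≈ 424. Laparoscopic arm: 848. The total of 1272 agrees with the stated 425 + 850 = 1275. At 425/850 the power is 80.1%. This figure is not in dispute.

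**3. Size of a possible bias (illustration)**

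Effect of radiotherapy: 8.2 − 2.4 = 5.8 points (section 4.5, about 2 years; carrying it to 3 years is an assumption). The between-arm difference in use, Δ, is also an assumption, because the documents give none. The bias in the recurrence difference is b = Δ × 5.8 points.

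- Power when open patients get more radiotherapy: Φ((0.05 − b)/SE − 1.96), with open 10% and laparoscopic 10% + b.
- Chance of wrongly passing when the true excess is 5 points and laparoscopic patients get more: Φ(b/SE − 1.96), with open 10% and laparoscopic 15% − b.

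For Δ = 10 points, b = 0.0058.

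- Power: SE = √(0.10×0.90/425 + 0.1058×0.8942/850) = 0.01797, giving Φ(0.0442/0.01797 − 1.96) = Φ(0.50) = 69.1%.
- Wrong pass: SE = √(0.10×0.90/425 + 0.1442×0.8558/850) = 0.01889, giving Φ(0.0058/0.01889 − 1.96) = Φ(−1.65) = 4.9%.

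| Assumed Δ in use | Bias (points) | Power, more use in open arm | Wrong pass, more use in laparoscopic arm |
|---|---|---|---|
| 0 | 0 | 80.1% | 2.5% |
| 5 | 0.29 | 74.9% | 3.5% |
| 10 | 0.58 | 69.1% | 4.9% |
| 20 | 1.16 | 56.3% | 9.0% |
| 30 | 1.74 | 43.0% | 15.2% |

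Each 10 points of Δ uses 0.58/5 ≈ 12% of the margin. A bias as large as the whole margin would need Δ = 5/5.8 ≈ 86 points.

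**The case against.** The strongest reply is that stratification already implies the order. A computer cannot generate an allocation stratified by radiotherapy until the stratum is known, so the yes/no decision, at least as planned, must come first. Section 14.1 also requires equal protocols in both arms, and a local protocol can include indications as well as doses. Using radiotherapy more readily in one arm would breach the intent of that rule.

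This reply stands in large part. A reader might infer that a center may randomize first, choose radiotherapy patient by patient afterwards, and still comply fully. The documents do not support that: such a center could not supply a stratum that three sections require. Nor does section 17.2 show that the decision follows allocation. It also lists date of diagnosis, tumor location and proposed resection, which would normally be known by then. The exclusion in section 9.2 of T4 tumors as staged before pre-operative therapy can be read as compatible with either order.

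A reader might also infer from section 4.5 that radiotherapy has the largest known effect on the endpoint. The protocol ranks no treatments, and section 4.2 reports local recurrence of up to 45% before TME and a significant drop after it.

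The reply does not remove the mismatch between sections 3.4, 5 and 10 and section 17.1, the silence on planned versus received therapy, or the discretion over schedule and chemotherapy. The web form may collect radiotherapy although section 17.1 omits it. The protocol does not say so.

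**Conclusion.** The point holds as an internal contradiction with a consequence for the primary comparison. Radiotherapy is declared a stratum, but the listed randomization entries cannot form it, so the protocol's own safeguard against arm-dependent radiotherapy is not secured. Schedule and pre-operative chemotherapy are outside the strata and rest on the equal-protocols rule alone.

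The authors probably intended the decision to come first, and nothing shows that imbalance will arise. If the stratum is applied as stated, planned use is balanced up to chance, and a gap in use would need departures from plan after allocation. The figures (0.58 point per 10 points of difference in use; 2.5% to 4.9% wrong pass, or 80% to about 69% power) therefore show sensitivity and are not a forecast. They assume that the 2-year effect carries to 3 years and that the gap arises only through knowledge of the arm. The power figure is about 70% if the standard error is held at its unbiased value.

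Section 19.1 names center as the only adjustment of the log-rank comparison. A separate analysis plan, not at hand, may add to that. The change is worth making because it is cheap and protects the primary endpoint.

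**What to change.** Reconcile section 17.1 with sections 3.4, 5 and 10:

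- Add to sections 10 and 17.1 a mandatory web entry for planned pre-operative radio- and/or chemotherapy (yes/no, and under which registered local protocol). It is completed before the allocation is released.
- State that the planned radiotherapy value so entered is the stratum, and use the same wording in all three stratification sentences.
- In section 19.1, include that stratum in the primary comparison alongside center.
- Record later departures from the entered plan with reasons, and report them by arm. Adjusting for the planned stratum does not correct for such departures, so they need to be visible.

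The cost is a few sentences and one web field. The sample size does not change. The small downside is that centers must wait for the treatment decision before they randomize. The change fixes only the order of decision and allocation, and no view is taken on which therapy to give.
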